4.3 Rationale for Study Population

The study population will be adults with a diagnosis of IgG4-RD who meet the 2019 ACR/EULAR classification criteria (Wallace et al, 2019b); who have had recent active disease (initial diagnosis or flare) requiring treatment; and who are at high risk of recurrent flare. The classification criteria have been demonstrated to have high specificity for the disease. The inclusion of patients at a high risk of disease recurrence, based on the number of involved organs, represents the population with the greatest medical need and permits a reasonable rate of accrual of events contributing to the efficacy endpoints (Khosroshahi et al, 2015; Omar et al, 2019; Abraham and Khosroshahi, 2017; Zhang and Stone, 2019). Active disease responds well and rapidly to GC therapy; however, recurrence of flare, with its attendant risk of progression of disease and of GC toxicity, requires an approach to the prevention, not just treatment, of disease flares.

The inclusion of subjects with recent active disease (either due to flare or initial diagnosis), serves to enroll patients at risk and to partially harmonize their treatment regimen at study entry. Because subjects have had a recent flare, they need to be appropriately treated but also, for purposes of study, be able to be safely taper and discontinue GCs. Thus, the protocol provides

limits to their GC therapy. To permit an 8-week completion of active disease treatment after randomization, patients must be able to tolerate 20 mg/day of prednisone or equivalent at randomization.

Patients are excluded for risks related to potential immunosuppression and for advanced renal disease or other serious illness that could alter the potential benefit-risk assessment. To avoid confounding interpretation of safety and efficacy data based on the use of prior immunosuppressive drugs, especially B-cell depletive agents, exclusion criteria provide limitations on prior therapy. Patients must have had baseline scans to permit assessment of disease activity and on-study comparisons.

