- 6. IgG4-RD affecting at least 2 organs/sites at any time in the course of IgG4-RD with documentation to confirm. One organ must meet the requirements for the ACR/EULAR classification criteria (inclusion 4); the second organ is as defined by the investigator.
- 7. Willing and able to comply with the protocol, complete study assessments, and complete the study period.
- 8. Non-sterilized male subjects who are sexually active with a female partner of childbearing potential must use a condom with spermicide (where spermicide is available) from Day 1 through to the end of the study and must agree to continue using such precautions for at least 6 months after the final dose of IP.

Females of childbearing potential must have a negative serum pregnancy test at screening. Females of childbearing potential who are sexually active with a non-sterilized male partner must use a highly effective method of contraception (Table 2) from signing informed consent and must agree to continue using such precautions through the end of the follow-up of the study and at least 180 days after the last dose of IP; cessation of contraception after this point should be discussed with a responsible physician. Periodic abstinence, the rhythm method, and the withdrawal method are not acceptable methods of contraception. A recommendation will be made that the female partners (of childbearing potential) of male study participants should use a highly effective method of contraception other than a barrier method.

Females of childbearing potential are defined as those who are not surgically sterile (ie, surgical sterilization includes bilateral tubal ligation, bilateral oophorectomy, or hysterectomy) or those who are not postmenopausal (defined as 12 months with no menses without an alternative medical cause and a follicle-stimulating hormone within the postmenopausal range as established by the clinical laboratory).

Table 2Highly Effective Methods of Contraception for Females of Childbearing
Potential

Physical Methods	Hormonal Methods
 Intrauterine device (IUD) Intrauterine hormone-releasing system (IUS) ^a 	• Combined (estrogen and progestogen-containing hormonal contraception)
 Bilateral tubal occlusion Vasectomized partner^b 	Oral (combined pill)Injectable
 Sexual abstinence ° 	• Transdermal (patch)
	 Progestogen-only hormonal contraception associated with inhibition of ovulation^d
	• Implantable
	• Intravaginal

a This is also considered to be a hormonal method.

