#### 2.2 Study Design

This is a multicenter, randomized, double-blind (Investigator, subject, and Sponsor will be blinded to treatment assignment), placebo-controlled, parallel-cohort study to evaluate the efficacy and safety of inebilizumab for prevention of disease flare in adults with active IgG4-RD who are at high risk of recurrent flare.

The study will be conducted at approximately 60-80 sites in 20 countries. The expected duration of each subject's participation in this study is up to 400 days (screening and RCP) or, for eligible subjects who enroll in the optional OLP, up to 2,273 days (screening, RCP, interval between RCP and OLP, and OLP). A safety follow-up period (SFP) of 2 years after the last IP dose will take place for subjects who do not enter the OLP or who discontinue IP during the OLP.

Subjects will be stratified by first or subsequent IgG4-RD manifestation (i.e., newlydiagnosed vs. recurrent) and randomized 1:1 by an interactive voice/web response system (IXRS) to one of two blinded treatment groups:

- Inebilizumab group: Subjects will receive an infusion of inebilizumab 300 mg IV on Day 1, Day 15, and at Week 26.
- Placebo group: Subjects will receive an infusion of placebo on Day 1, Day 15, and at Week 26.

During the 52-week RCP, subjects will attend monthly visits for study assessments and procedures. Suspicion of flare will trigger diagnostic assessments by the Investigator. The Investigator will determine if the event meets protocol defined criteria for flare, and, independent of the flare determination, will decide if the event requires treatment. The same data reviewed by the Investigator will also be evaluated by a central, independent, and blinded AC (blinded to treatment allocation and to investigator determination of meeting flare criteria or requiring treatment) that will determine whether protocol-defined flare criteria are met.

All subjects should be followed through the end of the RCP. A subject who decides to withdraw from the RCP should be asked to complete the final visit (early discontinuation visit [EDV]) for safety follow-up. Subjects who discontinue IP during the RCP without withdrawing from the study will remain in the RCP for its duration and complete the Day 365 visit.

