#### **Table 3 Baseline Characteristics**

- IgG4-RD manifestation (newly diagnosed vs recurrent) n (%)
- Disease duration (years) defined as the years between date of diagnosis and date of 1st administration of IP, calculated as (date of 1st IP administration date of diagnosis + 1)/365.25 descriptive statistics
- Number of organs ever affected by IgG4-RD (1, 2, 3, etc.)
- List of organs previously affected (meninges, pituitary gland, etc. "other" counts as 1) n (%)
- Highest known IgG4 serum level descriptive statistics
- Category of highest IgG4 serum level (< median vs  $\geq$  median) n (%)
- IgG4-RD RI descriptive statistics
- Prior non-glucocorticoid therapy for IgG4-RD (yes / no) n (%)

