The hazard rate in the inebilizumab group will be compared to that in the placebo group using the Cox proportional hazards model with the treatment indicator (inebilizumab or placebo) and the stratification factor as the explanatory variables. The HR of inebilizumab versus

placebo will be estimated together with its associated 95% CI. The two-sided p-value for the treatment effect will be determined using Cox proportional regression model. SAS PROC PHREG will be used for fitting this model.

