#### 3.5.2 Secondary Efficacy Endpoints and Analyses

The protocol defined 6 secondary efficacy endpoints. Endpoints 1, 2, and 3 are key secondary endpoints to be considered for study-wise Type I error control:

- 1. Annualized flare rate for treated and AC-determined IgG4-RD flares during the RCP.
- 2. The proportion of subjects achieving flare-free, treatment-free complete remission at Week 52,
- 3. The proportion of subjects achieving flare-free, corticosteroid-free complete remission at Week 52.
- 4. Time to initiation of first treatment (medication or procedure) for new or worsening disease activity by the Investigator within the RCP, regardless of AC determination of flare.
- 5. Annualized flare rate for AC-determined IgG4-RD flares, whether or not treated, during the RCP.
- 6. Glucocorticoid (GC) use, calculated as the cumulative GC dose taken for the purpose of IgG4-RD disease control during the RCP.
- 3.5.2.1 Annualized Flare Rate for treated and AC-determined IgG4-RD Flares During the RCP

The estimand with a treatment policy strategy is defined by the following:

• Target population: Subjects in the FAS

- Variable: The number of treated AC-determined IgG4-RD flares experienced during 52-week RCP
- Intercurrent event: No intercurrent events will be taken into account. All data captured during the 52-week RCP will be used for analysis.
- Population-level summary: Rate ratio between inebilizumab versus placebo and its associated 95% CI.

The number of treated and AC-determined flares will be compared between the inebilizumab group and the placebo group using a negative binomial model. The model will include covariates of treatment group (inebilizumab or placebo) and stratification factors. The logarithm of the subject's corresponding follow-up time will be used as an offset variable in the model to adjust for subjects having different exposure times during which the events occur. The estimated treatment effect (ie, the rate ratio of inebilizumab versus placebo), corresponding 95% CI, and two-sided p-value for the rate ratio will be presented.

In addition, the annualized flare rate and the corresponding 95% CI within each treatment group, and the absolute difference between treatment groups with the corresponding 95% CI, will be presented.

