An additional analysis may be conducted by considering subjects, who receive 1) any treatment for IgG4-RD, including GC or immunosuppressive treatment (other than GC tapered in accordance with the protocol-specified schedule during the first 8 weeks of the RCP) and/or 2) any prohibited GC or immunosuppressive treatment, to be censored at the time when relevant treatment was first received.

3.5.2.2 The Proportion of Subjects Achieving Flare-Free, Treatment-Free Complete Remission at Week 52

Flare-free, treatment-free complete remission is defined as lack of evident disease activity at Week 52, no AC-determined flare during the RCP, and no treatment for flare or disease control except the required 8-week GC taper. Lack of evident disease activity is defined as either an IgG4- RD Responder Index (Wallace et al, 2018) score of 0, or a determination by the investigator that no disease activity is present based on physical, laboratory, pathology or other evidence.

The estimand with a composite strategy is defined by the following:

- Target population: Subjects in the FAS
- Variable: Proportion of subjects achieving flare-free, treatment-free complete remission at Week 52
- Intercurrent event: Subjects who receive treatment for flare or disease control except the required 8-week GC taper will be treated as not achieving complete remission at Week 52.
- Population-level summary: Odds ratio between inebilizumab versus placebo and its associated 95% CI.

The results of the analyses will be presented using odds ratios, together with associated 95% CI and two-sided p-value. In addition, the absolute difference of the proportions between treatment groups with the corresponding 95% CI and two-sided p-value, will also be presented.

The estimate of the treatment effect will be assessed using a logistic regression model. The response variable in the model will be whether or not a subject achieves the corresponding flare-free treatment-free complete remission at Week 52. The model will have treatment indicator (inebilizumab or placebo) and stratification factor as the explanatory variables. SAS PROC LOGISTIC and PROC GENMOD with LOGIT link will be used for fitting this model and estimate odds ratio and absolute difference of the proportions, respectively.

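### Optional efficiency gain: the primary and key secondary models adjust only for newly diagnosed versus recurrent disease, although organ count and baseline Responder Index are available before dosing

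*SAP*

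**What the plan says.** **Models.** SAP 3.5.1.1 fits the primary Cox model with "the treatment indicator (inebilizumab or placebo) and the stratification factor as the explanatory variables". For the annualised flare rate, SAP 3.5.2.1 says: "The model will include covariates of treatment group (inebilizumab or placebo) and stratification factors", with log follow-up time as offset. For each remission endpoint, SAP 3.5.2.2 and 3.5.2.3 say: "The model will have treatment indicator (inebilizumab or placebo) and stratification factor as the explanatory variables". Protocol 9.5.1, 9.5.2.1 and 9.5.2.3 specify the same models.

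**Stratification.** SAP 2.2: "Subjects will be stratified by first or subsequent IgG4-RD manifestation", that is, newly diagnosed versus recurrent. Organ count plays no part in it.

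**Organ count and RI.** Protocol 4.3 explains the population by "The inclusion of patients at a high risk of disease recurrence, based on the number of involved organs". Inclusion criterion 6 turns this into a threshold: "IgG4-RD affecting at least 2 organs/sites at any time in the course of IgG4-RD with documentation to confirm". SAP Table 3 lists "Number of organs ever affected by IgG4-RD (1, 2, 3, etc" and "IgG4-RD RI descriptive statistics" among the baseline summaries. Protocol Table 4 schedules the RI on Day 1, before the infusion. Neither variable is in an efficacy model or in the subgroup lists of Protocol 9.5.4 and SAP 3.5.3.

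**The concern.** The plan measures two baseline quantities with a plausible link to outcome and then makes no use of them for efficacy.

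For organ count, Protocol 4.3 makes the link. Appendix D adds to it: several flare criteria are easier to meet in an organ that already has a disease history. In the biliary tree (4.11), a laboratory change alone is enough after earlier cholangitis, while a first episode also needs imaging or endoscopy. The pancreas (4.10) and kidney (4.12) criteria have the same shape, and endocrine dysfunction alone counts as a pituitary flare only in known pituitary disease (4.2).

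For RI, the link is to the remission endpoints, because an RI of 0 at Week 52 is one of the two ways to show no evident disease activity. Protocol 4.4 does not require complete remission at randomisation, so some spread at baseline is expected.

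At stake is efficiency. The plan expects 160 × 0.245 = 39.2 events against 39 required, so extra precision would be welcome if the covariates are prognostic.

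**Working it through.** **1. The plan's own figure.** Inputs from Protocol 9.3: HR 0.35, two-sided α 0.05, power 90%, 1:1 allocation, placebo flare probability 0.35.

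- Events (Schoenfeld): 4 × (1.960 + 1.2816)² / (ln 0.35)² = 38.1, rounded up to 39.
- Power with 39 events: Φ(√39 / 2 × 1.0498 − 1.960) = Φ(1.318) = 90.6%.
- Inebilizumab risk: 1 − exp(−0.1508) = 0.140. Mean risk: (0.35 + 0.140) / 2 = 0.245. N = 39 / 0.245 = 159.2, stated as 160.

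The design reproduces and takes no credit for covariate adjustment.

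**2. What adjustment could add.** The documents give no prognostic strength for either variable, so a range was simulated. From the plan: N = 160, 52 weeks, arm risks 0.35 and 0.14. Assumed: exponential times, no dropout, two equal strata without prognostic effect, standard normal covariates with correlation 0.3, and the stated HR per SD. Each row uses 4,000 trials and a Cox Wald test. The Monte Carlo SE of each power is about √(0.88 × 0.12 / 4000) = 0.5 points. Both models were fitted to the same simulated data.

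| Covariates added, assumed strength | Power, stratification only | Power, adjusted | Change (points) | Median HR | Mean SE of log HR |
|---|---|---|---|---|---|
| Organ count + RI, not prognostic | 88.3% | 88.2% | −0.1 | 0.345 → 0.343 | 0.366 → 0.368 |
| Organ count + RI, HR 1.25 each | 88.1% | 88.7% | +0.6 | 0.346 → 0.337 | 0.365 → 0.368 |
| Organ count + RI, HR 1.5 each | 88.8% | 91.6% | +2.8 | 0.344 → 0.319 | 0.365 → 0.370 |
| Organ count + RI, HR 2.0 each | 88.2% | 96.2% | +8.0 | 0.344 → 0.269 | 0.365 → 0.378 |
| Organ count only, HR 1.5 | 88.1% | 88.8% | +0.7 | 0.350 → 0.337 | 0.364 → 0.368 |

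The last row matches what is proposed for the Cox model. Nothing was simulated for the negative binomial or logistic models.

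**3. Where the gain comes from.** The SE rises slightly in every row. Power rises because the conditional log HR is larger. At HR 1.5 each, |ln 0.344| / 0.365 = 2.92 becomes |ln 0.319| / 0.370 = 3.09. With no prognostic value, |ln 0.345| / 0.366 and |ln 0.343| / 0.368 are both 2.91.

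**4. Alternative reading.** If 0.35 is taken as the covariate-conditional HR, the two-covariate changes are 88.0% → 88.1% (HR 1.25 each), 84.3% → 88.0% (1.5) and 77.3% → 89.4% (2.0). This reading makes the marginal effect weaker than planned, so the table above is closer to the protocol.

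**5. Feasibility.** Thirty-nine events give 13 per parameter with three terms in the Cox model (39 / 3), or about 10 with four. Under the null, rejection rates were 3.8% to 4.7% for the stratification-only model and 4.1% to 5.5% for the two-covariate model (3,000 trials per scenario).

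**The case against.** The planned analysis is complete and prespecified, adjusts for the randomisation stratum, and is the same in both documents. That stands: nothing here is an error.

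A reader might infer four stronger points, and the documents do not support them.

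- **That the trial is below its stated power.** The 39 events and 90% reproduce. The simulated 88% reflects a Wald test with a random event count and does not show the stated figure to be wrong.
- **That adjustment is free.** The SE rises slightly and the HR or odds ratio becomes conditional on more variables. SAP 3.1.1 leaves missing baseline values unimputed, so without a rule a subject lacking a covariate would drop out of the model and the analysis would no longer cover the full analysis set. Protocol text is also affected.
- **That the protocol treats organ count as the driver of flare risk.** It links count to risk and uses it as an entry threshold that every subject meets. It gives no gradient above two organs. The second organ is left to the investigator's definition, so the count is coarse. No section calls baseline RI prognostic for flare, and RI is measured after 3 to 8 weeks of glucocorticoid, which may narrow its spread.
- **That the planned HR and odds ratio are biased toward 1.** The difference from the adjusted value is non-collapsibility. The SAP defines its summary simply as the ratio between arms.

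On the other side, Appendix D gives organ history a role beyond the threshold, and the planned models already condition on one factor, so conditioning on another is a change of degree.

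**Conclusion.** The point holds as an optional efficiency improvement of low severity. The models leave out two baseline variables that the trial already collects and that have some support in the documents as relevant to outcome.

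For the primary endpoint, the expected gain from organ count alone is small: about 0.7 points of power at an assumed HR of 1.5 per SD, which is of the same order as the simulation error. Adding RI as well gives between −0.1 points (no prognostic value) and +2.8 (HR 1.5 per SD each), with +8.0 only if both are strong (2.0 per SD each).

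These figures rest on the assumed strengths, normal covariates, the 0.3 correlation, equal strata and no dropout. For the remission endpoints the case for RI is by reasoning, without a computed figure.

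**What to change.** Before unblinding:

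1. Add number of organs ever affected, as a continuous term, to the primary Cox model and to the negative binomial model for treated, adjudicated flares.
2. Add number of organs ever affected and baseline RI to both logistic models. Keep the stratification factor in all of them.
3. State the coding and a simple rule for a missing covariate, for example the pooled median of observed baseline values without regard to arm, so that every subject in the full analysis set stays in the model.
4. State that the HR, rate ratio and odds ratios are adjusted for these variables.
5. Keep the stratification-only models as sensitivity analyses.
6. Align Protocol 9.5.1 to 9.5.2.3.

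The cost is wording in two documents, with no new data collection. If the covariates turn out not to be prognostic, the loss is a few tenths of a point of power. The SE of the log HR grows slightly, and the HR or odds ratio is conditional on one or two more variables. A sponsor unwilling to change the confirmatory models could prespecify the adjusted models as supportive analyses. That would check robustness but would not recover power in the confirmatory tests.

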#### 3.5.1.2 Additional Analysis on the Primary Efficacy Endpoint

The estimand of the additional analysis is defined by the following:

- Target population: Subjects in the FAS
- Variable: Time in days from Day 1 (dosing) to the date of the first treated and ACdetermined IgG4-RD flare within the 52-week RCP. Date of flare onset is defined as date of onset of treatment (medication or procedure).
- Intercurrent event:
  - Subjects who do not complete the RCP and who have not had a treated and AC-determined flare will be censored at the time of discontinuation.
  - Subjects, who 1) receive any treatment for IgG4-RD, including GC or immunosuppressive treatment (other than GC tapered in accordance with the protocol-specified schedule during the first 8 weeks of the RCP) and/or 2) receive any prohibited GC or immunosuppressive treatment prior to experiencing a treated and AC-determined flare, will be censored at the time when relevant treatment was first received.
- Population-level summary: HR between inebilizumab versus placebo and its associated 95% CI.

The robustness towards violations of the assumption of non-informative censoring on subjects who do not complete the RCP and / or subjects who received prohibited GC or immunosuppressive treatment prior to experiencing a treated and AC-determined flare will be assessed with the following sensitivity analysis:

- Target population: Subjects in the FAS
- Variable: Time in days from Day 1 (dosing) to the date of the first treated and ACdetermined IgG4-RD flare within the 52-week RCP. Date of flare onset is defined as date of onset of treatment (medication or procedure).
- Intercurrent event:
  - Subjects who do not complete the RCP due to IgG4-RD related death or due to subject perception of lack of efficacy and who have not had a treated and ACdetermined flare will be considered as having a flare at the time of discontinuation / withdrawal from RCP. Subjects who do not complete the RCP due to other reasons and who have not had a treated and AC-determined flare will be censored at the time of discontinuation / withdrawal from RCP.
  - Subjects who receive the treatment for IgG4-RD, including GC or immunosuppressive treatment (other than GC tapered in accordance with the protocol-specified schedule during the first 8 weeks of the RCP) related to IgG4-RD prior to experiencing a treated and AC-determined flare will be considered as having a flare at the time of treatment.

- Subjects who receive any prohibited GC or immunosuppressive treatment not related to IgG4-RD prior to experiencing a treated and AC-determined flare will be censored at the time when those treatment were first received.
- Population-level summary: HR between inebilizumab versus placebo and its associated 95% CI.

To assess the impact of immortal time bias, the following analysis will be performed:

- Target population: Subjects in the FAS
- Variable: Time in days from Day 1 (dosing) to the date of the first treated and ACdetermined IgG4-RD flare within the 52-week RCP. Date of flare onset is defined as earliest date of subject reported new/worsening symptoms, new/worsening physical exam findings, new/worsening laboratory findings, new/worsening findings imaging, or other findings as data collected on flare assessment page.
- Intercurrent event: All data captured during the 52-week RCP will be used for analysis. Subjects who do not complete the RCP and who have not had a treated and AC-determined flare during the RCP will be censored at the time of discontinuation.
- Population-level summary: Hazard ratio (HR) between inebilizumab versus placebo and its associated 95% CI.

Data will be analyzed using the same Cox proportional hazards model as that for the primary efficacy analysis. The HR of inebilizumab versus placebo will be estimated together with its associated 95% CI and the corresponding p value.

